10.1.2. Financial Disclosure

Investigators and Subinvestigators will provide Alexion with sufficient, accurate financial information as requested to allow Alexion to submit complete and accurate financial certification or disclosure statements to the appropriate regulatory authorities. Investigators are responsible for providing information on financial interests during the course of the study and for 1 year after completion of the study.

10.1.3. Informed Consent Process

- It is the responsibility of the Investigator to obtain signed (written or electronic signature) informed consent from all study participants prior to any study-related procedures including screening assessments.
- The Investigator or his/her representative will explain the nature of the study (including but not limited to the objectives, potential benefits and risks, inconveniences, and the participant's rights and responsibilities) to the participant or his/her legally authorized representative, defined according to local and country regulations where the study is taking place, and answer all questions regarding the study.
- Participants must be informed that their participation is voluntary. Participants or their legally authorized representative will be required to sign a statement of informed consent or a certified translation if applicable, that meets the requirements of 21 CFR 50, local regulations, EU General Data Protection Regulation (GDPR), ICH guidelines, Health Insurance Portability and Accountability Act (HIPAA) requirements, where applicable, and the IRB/IEC or study center.
- The medical record must include a statement that signed (written or electronic) informed consent was obtained before the participant was screened in the study and the date the written consent was obtained. The authorized person obtaining the informed consent must also sign the ICF/ICFs.
- Participants must be re-consented to the most current version of the ICF/ICFs during their participation in the study.
- A copy of the signed (written or electronic) informed consent documentation (ie, a complete set of participant information sheets and fully executed signature pages) must be provided to the participant or the participant's legally authorized representative, as applicable. This document may require translation into the local language. Signed (written or electronic) consent [or assent] forms must remain in each participant's study file and must be available for verification at any time.

The ICF will contain a separate section that addresses the use of remaining mandatory samples for optional exploratory research. The Investigator or authorized designee will explain to each participant or their legally authorized representative the objectives of the exploratory research. If sharing exploratory research results with the Investigator is not planned, the ICF should mention it. Participants or their legally authorized representative will be told that they are free to refuse to participate and may withdraw their consent at any time and for any reason during the storage period. A separate signature will be required to document a participant's agreement to allow any remaining specimens to be used for exploratory research. Participants who decline to participate in this optional research will not provide this separate signature.

10.1.4. Data Protection

- Participants will be assigned a unique identifier by Alexion. Any participant records or datasets that are transferred to Alexion will contain the identifier only; participant

names or any information which would make the participant identifiable will not be transferred.

- Participants must be informed that their personal study-related data will be used by Alexion in accordance with local data protection law. The level of disclosure must also be explained to the participants who will be required to give consent for their data to be used as described in the informed consent.
- Participants must be informed that their medical records may be examined by Clinical Quality Assurance auditors or other authorized personnel appointed by Alexion, appropriate IRB/IEC members, and inspectors from regulatory authorities.

10.1.5. Dissemination of Clinical Study Data

Study-related information and study results may be posted on publicly accessible clinical study databases (eg, www.clinicaltrials.gov or www.clinicaltrialsregister.eu), as appropriate, and in accordance with national, regional, and local regulations.

10.1.6. Data Quality Assurance

- All participant data relating to the study will be recorded on printed or electronic CRF unless transmitted to Alexion or designee electronically (eg, laboratory data). The Investigator is responsible for verifying that data entries are accurate and correct by physically or electronically signing the CRF.
- The Investigator must maintain accurate documentation (source data) that supports the information entered in the CRF.
- The Investigator must permit study-related monitoring, audits, IRB/IEC review, and regulatory agency inspections and provide direct access to source data documents.
- Alexion or designee is responsible for the data management of this study including quality checking of the data.
- Study monitors will perform ongoing source data verification to confirm that data entered into the CRF by authorized site personnel are accurate, complete, and verifiable from source documents; that the safety and rights of participants are being protected; and that the study is being conducted in accordance with the currently approved protocol and any other study agreements, ICH GCP, and all applicable regulatory requirements.
- Records and documents, including signed ICFs, pertaining to the conduct of this study must be retained by the Investigator for a minimum of 25 years after study completion, unless local regulations or institutional policies require a longer retention period. No records may be destroyed during the retention period without the written approval of Alexion. No records may be transferred to another location or party without written notification to Alexion.

10.1.7. Source Documents

Source documents provide evidence for the existence of the participant and substantiate the integrity of the data collected. The Investigator or designee will prepare and maintain adequate

and accurate source documents (eg, medical records, ECGs, AE and concomitant medication reporting, raw data collection forms) designed to record all observations and other pertinent data for each participant.

Data reported on the CRF that are transcribed from source documents must be consistent with the source documents or the discrepancies must be explained. The Investigator may need to request previous medical records or transfer records, depending on the study. Also, current medical records must be available. Source documents are filed at the Investigator's site.

10.1.8. Study and Site Start and Closure

The study start date is the date on which the first participant is consented.

Alexion reserves the right to close the study site or terminate the study at any time for any reason at the sole discretion of Alexion. Study sites will be closed after the study is completed or following the decision to close or terminate the study. A study site is considered closed when all participants have completed the end of study or early discontinuation visit, all data have been collected and entered into electronic data capture (EDC) system, all required documents and study supplies have been collected, and a study-site closure visit has been performed.

The Investigator may initiate study-site closure at any time, provided there is reasonable cause and sufficient notice is given in advance of the intended termination.

Reasons for the early closure of a study site by Alexion or Investigator may include but are not limited to:

- Failure of the Investigator to comply with the protocol, the requirements of the IRB/IEC or local health authorities, Alexion's procedures, or GCP guidelines
- Inadequate recruitment of participants by the Investigator
- Discontinuation of further study intervention development

If the study is prematurely terminated or suspended, Alexion shall promptly inform the Investigators, the IECs/IRBs, the regulatory authorities, and any contract research organization(s) used in the study of the reason for termination or suspension, as specified by the applicable regulatory requirements. The Investigator shall promptly inform the participant and should assure appropriate participant therapy and/or follow-up.

10.1.9. Publication Policy

The full terms regarding publication of the results of this study are outlined in the applicable Clinical Study Agreement.

10.2. Clinical Laboratory Tests

- The tests detailed in [Table 9](#) will be performed by the local laboratory.
- Protocol-specific requirements for inclusion or exclusion of participants are detailed in [Section 5](#).
- Additional tests may be performed at any time during the study as determined necessary by the Investigator or required by local regulations.
- Pregnancy testing: Women of childbearing potential should only be enrolled after a negative serum pregnancy test result at Screening. Additional urine pregnancy testing will be standard for the protocol unless serum testing is required by site policies, local regulation, or IRB/IEC and should be performed per the time points specified in the SoA ([Section 1.3](#)). Screening pregnancy criteria are detailed in [Section 5.1](#).

Table 9: Protocol-Required Safety Laboratory Assessments

Clinical Chemistry	
Blood urea nitrogen (BUN)	Alanine aminotransferase
Potassium	Alkaline phosphatase
Creatinine	Urea
Creatine kinase	Magnesium
Sodium	Iron
Chloride	Zinc
Potassium	Total and direct bilirubin
Glucose	Total protein
Total carbon dioxide	Albumin
Aspartate aminotransferase	Calcium
Gamma glutamyltransferase	Phosphate
Hematology	
Hematocrit	Red blood cell count ^a
Platelets	Mean corpuscular volume
White blood cell count	Mean cell hemoglobin concentration
Mean cell hemoglobin	Lymphocytes
Neutrophils	Eosinophils
Monocytes	Prothrombin time
Basophils	International normalized ratio
Hemoglobin	Partial thromboplastin time
Urinalysis	
Bilirubin	Blood
Glucose	Ketones
Leukocytes	Microscopy
Nitrite	pH
Protein	Specific gravity
Urobilinogen	Red blood cells
Bacteria	
Other Tests	
HIV, hepatitis B, and hepatitis C screen	Total copper and total molybdenum
Ceruloplasmin (serum and plasma)	PUF-molybdenum and PUF-copper
Ceruloplasmin-bound copper	Labile bound copper
24-hour urine copper and molybdenum	Serum and urine pregnancy test
Urine drug screen	

^a Including nucleated red blood cells.

Details of liver chemistry stopping criteria and required actions and follow-up assessments after liver stopping or monitoring event are given in Section 6.6. All events of alanine aminotransferase (ALT) $\geq 3 \times$ upper limit of normal (ULN) and bilirubin $\geq 2 \times$ ULN ($> 35\%$ direct bilirubin) or ALT $\geq 3 \times$ ULN and international normalized ratio (INR) > 1.5 , if INR measured which may indicate severe liver injury (possible Hy's Law), must be reported as an SAE (excluding studies of hepatic impairment or cirrhosis).

Abbreviations: HIV= human immunodeficiency virus; PUF = plasma ultrafiltrate; SAE = serious adverse event.

Investigators must document their review of each laboratory safety report.

10.3. Adverse Events: Definitions and Procedures for Recording, Evaluating, Follow-up, and Reporting

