5.2. Exclusion Criteria

Medical Conditions

1. Decompensated cirrhosis or model for end-stage liver disease (MELD) score > 13.
2. Modified Nazer score > 7 (Dhawan, 2005).
3. Clinically significant gastrointestinal bleed within past 3 months.
4. Alanine aminotransferase (ALT) > 2 × upper limit of normal (ULN).
5. Marked neurological disease requiring assistance with self-care or activities of daily life.
6. Hemoglobin less than lower limit of the reference range for age and sex.
7. Active infection with hepatitis B virus (positive hepatitis B surface antigen) or C virus (participants with positive hepatitis C antibody result would require confirmation of active disease with a positive hepatitis C polymerase chain reaction test), or seropositivity for human immunodeficiency virus (HIV).

8. History or presence of/significant history of or current cardiovascular, respiratory, hepatic, renal, gastrointestinal, endocrinological, hematological, or neurological disorders, or psychiatric disorder that in the opinion of the Investigator may constitute a risk when taking the study intervention; or may interfere with the interpretation of data.

Prior/Concomitant Therapy

9. Previous treatment with ALXN1840 or other form of tetrathiomolybdate within 1 year prior to dosing.
10. Previous treatment with zinc within 21 days prior to Day 1.

Prior/Concurrent Clinical Study Experience

11. The use of an experimental or unapproved/unlicensed therapy at the same time or within 90 days or 5 half-lives, whichever is longer, prior to the Screening Visit.

Diagnostic Assessments

12. Participants in renal failure, defined as in end-stage renal disease on dialysis (chronic kidney disease [CKD] stage 5) or creatinine clearance < 30 mL/min (Levey, 2006).

Other Exclusions

13. Pregnant (or females who are planning to become pregnant) or breastfeeding females (women of childbearing potential must have a negative serum pregnancy test result at screening).
14. Known sensitivity to ALXN1840, ALXN1840 excipients (anhydrous dicalcium phosphate, anhydrous sodium carbonate), or any of the ingredients contained in ALXN1840 or related compounds.
15. In the opinion of the Investigator, the participant and/or their legal guardian is likely to be non-compliant or uncooperative during the study.

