6.6. Dose Modification

Participants will be initiated on ALXN1840 at 15 mg once daily and increased to 30 mg once daily on Day 29. Specific criteria for dose reduction, temporary interruption of dosing, or restriction of dose increases of ALXN1840 are detailed in [Table 7](#). Repeat testing of parameters meeting dose modification criteria should follow the instructions in [Table 7](#). Results from non-scheduled safety laboratory assessments must be recorded in the CRF.

Alexion should be notified within 24 hours of any laboratory, vital sign, electrocardiogram (ECG) abnormality, or AE that are considered of clinical concern by the Investigator. Investigators must notify Alexion immediately of study intervention discontinuation. The decision to discontinue study intervention should not be delayed for causality assessment.

Table 7: ALXN1840 Dose Modifications for Individual Participants

Test	Result	Conditions	Action with ALXN1840 Dosing	Changes in Safety Monitoring ^a	Rechallenge ^{b,c,d}
ALT	> 5 × ↑ from baseline	ALT above reference range at baseline	Temporary interruption	Contact participant within 48 hours to arrange repeat testing (weekly repeat testing)	At 15 mg QOD when ALT < 2 × ↑ from baseline.
	> 5 × ULN	ALT within reference range at baseline	Temporary interruption	Contact participant within 48 hours to arrange repeat testing (weekly repeat testing)	At 15 mg QOD when ALT < 2 × ULN.
	> 2 × ↑ from baseline	ALT above reference range at baseline	Reduce dose to previous dose level if up-titration has occurred or reduce dose to 15 mg QOD if on 15 mg QD. No further dose ↑ until resolution of abnormality.	Weekly repeat testing	Not applicable.
	> 2 × ULN	ALT within reference range at baseline	Reduce dose to previous dose level if up-titration has occurred or reduce dose to 15 mg QOD if on 15 mg QD. No further dose ↑ until resolution of abnormality.	Weekly repeat testing	Not applicable.
Hemoglobin	< 8 g/dL in the absence of bleeding	None	Temporary interruption	Weekly repeat testing	At 15 mg QOD when hemoglobin and other hematology parameters (neutrophils and platelets) are at baseline concentration.
	> 30% ↓ from baseline	None	Reduce dose to previous dose level if up-titration has occurred or reduce dose to 15 mg QOD if on 15 mg QD. No further dose ↑ until resolution of abnormality.	Weekly repeat testing	Not applicable.

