Platelets	< 30,000 μL	None	Temporary interruption	Weekly repeat testing	At 15 mg QOD when platelets and other hematology parameters (neutrophils and hemoglobin) are at baseline concentration.
	> 30% ↓ from baseline	Platelets below reference range at baseline	Reduce dose to previous dose level if up-titration has occurred or reduce dose to 15 mg QOD if on 15 mg QD. No further dose ↑ until resolution of abnormality.	Weekly repeat testing	Not applicable.
Neutrophils	< 1.0 × 10 ³ /μL	None	Temporary interruption	Weekly repeat testing	At 15 mg QOD when neutrophils and other hematology parameters

Test	Result	Conditions	Action with ALXN1840 Dosing	Changes in Safety Monitoring ^a	Rechallenge ^{b,c,d}
					(hemoglobin and platelets) are at baseline concentration.
	> 30% ↓ from baseline	Neutrophils below reference range at baseline	Reduce dose to previous dose level if up-titration has occurred or reduce dose to 15 mg QOD if on 15 mg QD. No further dose ↑ until resolution of abnormality.	Weekly repeat testing	Not applicable.
Bilirubin	> 2 × ULN	Accompanied by ALT > 3 × ULN, indicative of liver injury	Temporary interruption	Weekly repeat testing	At 15 mg QOD or less frequent, when bilirubin is below ULN. Rechallenge under these conditions requires approval of the Alexion Medical Monitor.
Neurological assessment	Evidence of neurologic worsening by AEs or by neurologic physical exam assessment		Investigator and Alexion Medical Monitor will evaluate the need for dose modification (interruption, increase or decrease) based on copper control parameters and relevant clinical data. Rationale for dosing decision must be documented in study record and re-evaluated at the next study visit.	All neurologic worsening should be documented as AEs and followed up until study completion or resolution of symptoms.	Discuss with the Alexion Medical Monitor.

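### Table 7 has no INR criterion, so ALT ≥ 3 × ULN with INR > 1.5 is not interrupted by rule until ALT passes 5 × ULN (or 5 × a raised baseline)

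*Protocol*

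**What the plan says.** - **Protocol 10.2, note to Table 9.** "Details of liver chemistry stopping criteria and required actions and follow-up assessments after liver stopping or monitoring event are given in Section 6.6". The next sentence names two patterns of possible Hy's Law: ALT ≥ 3 × ULN with bilirubin ≥ 2 × ULN (more than 35% direct), and ALT ≥ 3 × ULN with INR > 1.5. The second carries the qualifier "if INR measured which may indicate severe liver injury". The consequence attached to both is that they "must be reported as an SAE (excluding studies of hepatic impairment or cirrhosis"). INR is one of the Table 9 tests.
- **Protocol 6.6, Table 7, bilirubin row.** Bilirubin > 2 × ULN, with the condition "Accompanied by ALT > 3 × ULN, indicative of liver injury", leads to temporary interruption and weekly testing. On restarting: "Rechallenge under these conditions requires approval of the Alexion Medical Monitor".
- **Protocol 6.6, Table 7, ALT rows.** With a normal baseline ALT, dosing is interrupted above 5 × ULN. Above 2 × ULN the action is "Reduce dose to previous dose level if up-titration has occurred or reduce dose to 15 mg QOD if on 15 mg QD", with no further increase until resolution and weekly testing. With a raised baseline ALT the same two steps apply to multiples of baseline.
- **INR in Table 7.** No row mentions it.
- **Protocol 5.2.** ALT above 2 × ULN is excluded, so a baseline of up to 2 × ULN is eligible. Decompensated cirrhosis is excluded; compensated cirrhosis is not excluded as such.
- **Protocol 7.1.** The Investigator should consider discontinuation for abnormal liver function when a dose modification condition is met, or when it is in the participant's best interest.

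**The concern.** Section 10.2 gives the two patterns the same clinical meaning and refers to 6.6 for stopping criteria. The table found there acts on one of them by rule and is silent on the other. At the same ALT, a participant whose bilirubin rises has dosing held. A participant whose INR rises has the dose reduced or, in a narrow range, meets no laboratory row.

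What is at stake is continued dosing during a possible severe liver injury. Table 3 of the Protocol describes dose-dependent transaminase elevations, generally mild to moderate and reversible with dose adjustment, usually after 3 to 6 weeks. That is Days 21 to 42, which includes all 11 days at 30 mg (39 − 29 + 1 = 11).

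**Working it through.** The plan gives no figure to reproduce. The check applies the Table 7 rows to the INR pattern.

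**Inputs**
- INR pattern: ALT ≥ 3 × ULN with INR > 1.5 (10.2).
- Bilirubin not above 2 × ULN, so the bilirubin row is not met. Hematology rows are also taken as not met.
- Baseline ALT *b*, in multiples of ULN, at most 2.0 (5.2).
- On-treatment ALT *a*, in multiples of ULN.
- Table 7 cut-offs: for a normal baseline, reduce if *a* > 2 and interrupt if *a* > 5. For a raised baseline, reduce if *a*/*b* > 2 and interrupt if *a*/*b* > 5.

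**Formulas for a raised baseline**
- No ALT row is met while 3 ≤ *a* ≤ 2*b*. This needs 2*b* ≥ 3. At *b* = 1.5 exactly, only *a* = 3.0 is missed, so the band opens for *b* above 1.5.
- Reduction is the listed action from there up to 5*b*, and interruption follows above 5*b*.

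**Results (ALT in × ULN)**

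| Baseline ALT | No ALT row | Reduction listed | Interruption by ALT alone |
|---|---|---|---|
| Normal | none | 3.0 to 5.0 | above 5.0 |
| 1.2 | none (2 × 1.2 = 2.4) | 3.0 to 6.0 | above 6.0 |
| 1.4 | none (2 × 1.4 = 2.8) | 3.0 to 7.0 | above 7.0 |
| 1.6 | 3.0 to 3.2 | above 3.2 to 8.0 | above 8.0 |
| 1.8 | 3.0 to 3.6 | above 3.6 to 9.0 | above 9.0 |
| 2.0 | 3.0 to 4.0 | above 4.0 to 10.0 | above 10.0 |

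With bilirubin above 2 × ULN, every one of these baselines is interrupted once ALT is above 3.0. Table 7 uses strict inequalities where 10.2 uses ≥; nothing here rests on that difference.

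**Two examples**
- Normal baseline, ALT 4 × ULN. With bilirubin 2.1 × ULN, dosing is interrupted. With bilirubin 1.5 × ULN and INR 1.6, the listed action is reduction: 30 to 15 mg/day, or 15 mg daily to every other day.
- Baseline 1.8, ALT 3.5 × ULN (3.5/1.8 = 1.94-fold). With bilirubin 2.1 × ULN, dosing is interrupted. With bilirubin 1.5 × ULN and INR 1.6, no ALT or bilirubin row is met.

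**Other reading of the raised-baseline rows.** If the rise itself must exceed twice baseline, the cut-offs become 3*b* and 6*b*. The no-row band then opens for every raised baseline and is wider: 3.0 to 3.6 at *b* = 1.2 (3 × 1.2) and 3.0 to 6.0 at *b* = 2.0 (3 × 2.0). ALT-only interruption moves to above 12.0 at *b* = 2.0 (6 × 2.0). The table therefore uses the reading that gives the smaller gap.

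**The case against.** The strongest reply is that the two sections do different jobs. The Hy's Law sentence in 10.2 sets an SAE-reporting rule, qualified by whether INR was measured and by an exclusion for studies of hepatic impairment or cirrhosis. Section 6.6 does supply stopping criteria, and nothing says every reporting pattern needs its own dosing row. This stands: a reader might infer that the two sections contradict each other, and they do not. The point concerns an incomplete action table.

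A reader might also infer that the INR pattern is never interrupted. The ALT-only rows do interrupt it above 5 × ULN or 5 × baseline. Nor does the lower range amount to reduction and nothing more. Table 7 adds a bar on increase and weekly testing, and meeting any of its rows brings in the 7.1 instruction to consider discontinuation.

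In the no-row band, participants would not go without medical response. Where the reporting rule applies, the event is an SAE notified within 24 hours. Section 6.6 adds "Alexion should be notified within 24 hours of any laboratory, vital sign, electrocardiogram (ECG) abnormality, or AE" judged to be of clinical concern, and Section 8 calls for immediate discussion of immediate safety concerns. What is missing is a defined action: none of these sets one for INR.

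Finally, the stated safety review before titration covers data through Day 23, while laboratory tests are also drawn on Day 28. A reader might infer that escalation could ignore the Day 28 results. The documents do not support that. Table 7's bar on increase is not tied to a visit, the Safety Review Committee meets at the end of 15 mg dosing, tests are local, and the Investigator must review each report.

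**Conclusion.** The gap is real and minor. Table 7 sets no action on INR, so one of the two patterns that 10.2 calls possible Hy's Law is held by rule only at a much higher ALT than the other: above 5 × ULN for a normal baseline, and up to above 10 × ULN for a baseline of 2.0. For baselines above 1.5 and up to 2 × ULN, a band reaching at most 4 × ULN may meet no laboratory row. That leaves SAE reporting, where the rule applies, and Investigator and sponsor judgement.

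This rests on the 2-fold reading of the raised-baseline rows, on bilirubin not above 2 × ULN, on no hematology row being met, and on a baseline ALT within the entry limit. The combination is unlikely among about 10 participants, and the primary endpoint is unaffected. The case for change is a cheap gain in participant safety.

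**What to change.** Extend the Table 7 bilirubin row, keeping its present recovery condition for the bilirubin pattern, with wording such as:

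> *or ALT ≥ 3 × ULN with INR > 1.5 if baseline INR was ≤ 1.5 (if it was higher, a confirmed rise from baseline judged with the Medical Monitor): temporary interruption; weekly repeat testing; rechallenge at 15 mg QOD or less often, with Medical Monitor approval, once INR is back to baseline.*

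The baseline-INR condition is needed because compensated cirrhosis can be enrolled and 5.2 states no explicit INR limit. It does limit MELD and modified Nazer scores, but the documents do not give their components. Without the condition, a participant with a stable INR of 1.6 would be interrupted on a 1.5-fold ALT rise (3.0/2.0). For participants with a higher baseline INR the rule still relies on judgement, but it names who decides and on what.

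No new tests are required. INR is in Table 9, coagulation is already drawn on Days -8, -1, 8, 23 and 28 (Schedule of Activities, note r), and SAP 7.1.3.2 lists INR as a baseline characteristic. The cost is a slightly longer row and a rare extra interruption, with possible loss of some balance data in about 10 participants.

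As an optional clarification, one sentence could say that Day 28 laboratory results are checked against Table 7 before the first 30 mg dose.
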